#### 4.3.3.6 PATIENT SATISFACTION QUESTIONNAIRE (PSQ)

The study subjects will be asked to complete Subject Satisfaction Surveys (see **Attachment A**) at the 180-day follow-up visit.

#### 4.3.3.7 INDEPENDENT PHOTOGRAPHIC REVIEW

Three experienced, blinded photographic reviewers will perform a qualitative analysis/review of pre-treatment and post-treatment sets of images for each subject. Images will be provided in a blinded and randomized order. Each blinded reviewer will choose which side of the chest was treated with Renuvion. Success will be correct identification of treated side of the chest by at least 2 of the 3 reviewers.

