## 2.2 POTENTIAL RISKS AND BENEFITS

### 2.2.1 POTENTIAL RISKS

This treatment modality was designed to inherently minimize the risk to the subject. However, treatment with energy-based modalities (laser, radiofrequency, and plasma devices) produce subsequent heating of the soft tissue that could involve the following commonly Expected Treatment Effects (ETEs): discomfort/pain, edema, erythema, ecchymosis, hypoesthesia, temporary sensory nerve injury (touch sensitivity, itching, temporary numbness/tingling), transient migratory firmness, and temporary and/or transient crepitus.

In addition to commonly expected treatment effects, treatment with the Renuvion APR device could involve the following risks: helium embolism into the surgical site due to inadvertent introduction into the venous or arterial blood supply system, unintended burns (deep or superficial), pneumothorax, pneumomediastinum, temporary or permanent motor nerve injury, ischemia, fibrosis, infection, gas buildup, bleeding, hematoma, seroma, subcutaneous induration, pigmentation changes, increased healing time, unsatisfactory scarring, asymmetry and/or unacceptable cosmetic result.

Risks associated with tumescent anesthesia (lidocaine and epinephrine) include blurred vision, mental/mood changes, drowsiness, dizziness, unusually slow heartbeat, rash, itching, swelling, anxiety, apprehensiveness, restlessness, tremor, weakness, sweating, palpitations, pallor, nausea and vomiting, headache, and respiratory difficulties.

Subjects using drugs that reduce coagulation (aspirin or NSAIDs) may experience increased bruising or bleeding at the treatment site. Any other medications prescribed for the procedure or after-procedure by the investigator have their own risks; these risks should be discussed with the subject.

A grounding pad is used to ground/neutralize the electrical current. Subjects undergoing radiofrequency treatment will be kept away from contact with metal parts which are grounded, or which have appreciable capacitance to earth.

As the Investigator will be treating the subjects per their Standard Practice of Care, there may be additional risks associated with the gynecomastia procedure. The Investigator will be responsible for properly reviewing all potential risks with the patient prior to treatment.

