### 2.2.2 POTENTIAL BENEFITS

This study is being conducted to determine if there is a possible benefit of using the Renuvion APR device as an adjunct procedure to Gynecomastia surgery.

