##### **4.3.2 ADDITIONAL ENDPOINTS**

Other additional endpoints for this study are as follows:

1. Bilateral analysis of change to STPTUP (Tebbetts & Adams High 5 Measurements) from baseline to day 30, 90, and 180.
2. Bilateral analysis of change to STPTIMF (Tebbetts & Adams High 5 Measurements) from baseline to day 30, 90, and 180.
3. Bilateral analysis of male chest measurements (Murphy) from baseline to day 30, 90, and 180.
4. Bilateral analysis of skin excised during the procedure by Gynecomastia Grade (Rohrich Classification).
5. Bilateral analysis of gland tissue removal methods (Longheu) during the procedure by Gynecomastia Grade.
6. The Principal Investigator, sub-investigator or qualified clinician delegated by the principal investigator, will complete a bilateral PGAIS assessing overall aesthetic improvement in the treatment area at day 30, 90, and 180 post-treatment.
7. The subject will complete a bilateral SGAIS assessing overall aesthetic improvement in the treatment area at day 30, 90, and 180 post-treatment.
8. The subject will complete a bilateral Patient Satisfaction Questionnaire (PSQ) at the 180-day follow-up visit.

9. Baseline images compared to Day 30, 90, and 180 images will be assessed for correct identification of Renuvion-treated side by blinded IPRs.

[figure not shown]

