**TABLE 5: MODIFIED GLOBAL AESTHETIC IMPROVEMENT SCALE EVALUATION - SUBJECT**

Rating	
Very much improved	
Much improved	
Improved	
No change	
Worse	
Much worse	
Very much worse	

The Global Aesthetic Improvement Scale (GAIS) is a 5-point scale that rates global aesthetic improvement from the pretreatment appearance. The ratings are worse, no change, improved, much improved, and very much improved. It was validated by [name], et al. for this use. In this study both live observation and photo review are utilized by the physician or a qualified, delegated clinician and subject in order to assign a score. The PGAIS must be performed by the principal investigator, sub-investigator or qualified clinician delegated by the principal investigator. Both the PGAIS and SGAIS should be completed in two steps:

- Based on a live assessment of the subject while referring to the subject's pre-treatment photographs (subjects should be given a hand mirror for assessment); and
- Based on a comparison of the subject's pre-treatment photographs to the current post-treatment photographs.

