## 7.2 STUDY PROCEDURE

The bilateral gynecomastia surgery and Renuvion APR System use will be as per investigator's standard clinical practice. During the procedure, fat transfer and treatment of the lateral chest and/or axilla is not allowed. The Renuvion APR System will be used on one side only, and alternate consecutively between patients, starting on the right side. For example, subject 001 will be treated with Renuvion on the right side, subject 002, will be treated on the left, subject 003 will be treated on the right, etc. This treatment scheme will continue until enrollment has completed at each site. The subjects will be blinded as to which side has been treated with Renuvion.

Procedure data and adverse events will be captured.

Endermology is not allowed post-procedure for the duration of the study.

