## ATTACHMENTS: OUTCOME MEASURES

### ATTACHMENT A: PATIENT SATISFACTION QUESTIONNAIRE

*Please have the subject complete this assessment while referring to their image in the mirror and current post-treatment photos compared to baseline photos. Provide the subject with a mirror.*

*Using a mirror and reviewing your post-treatment photos, compare how your treatment area currently looks compared to your pre-treatment photos.*

1. On your **RIGHT** side, which, if any, changes do you see in the area treated?

- Less sagging skin
- Smoother skin texture
- Skin Feels Better
- Skin Feels Tighter
- Skin Appears Tighter
- Skin Looks more Radiant
- Skin Seems more Youthful
- Other: \_\_\_\_\_
- None

2. On your **LEFT** side, which, if any, changes do you see in the area treated?

- Less sagging skin
- Smoother skin texture
- Skin Feels Better
- Skin Feels Tighter
- Skin Appears Tighter
- Skin Looks more Radiant
- Skin Seems more Youthful
- Other: \_\_\_\_\_
- None

3. How would you characterize your satisfaction with the treatment on your **RIGHT** side?

- Very Satisfied
- Satisfied
- Slightly Satisfied
- Neither Satisfied or Dissatisfied
- Slightly Dissatisfied
- Dissatisfied
- Very Dissatisfied

4. How would you characterize your satisfaction with the treatment on your **LEFT** side?

- Very Satisfied
- Satisfied
- Slightly Satisfied
- Neither Satisfied or Dissatisfied
- Slightly Dissatisfied
- Dissatisfied
- Very Dissatisfied

5. Do you feel that one side of your chest looks better than the other (check one)?

YES       NO

a. If Yes, which side do you like better?

RIGHT       LEFT

6. Do you feel that the skin on one side of your chest feels tighter than the other (check one)?

YES       NO

a. If Yes, which side does the skin feel tighter?

RIGHT       LEFT

7. Do you feel the skin quality on one side of your chest is better than the other (check one)?

YES       NO

a. If Yes, which side has better skin quality?

RIGHT       LEFT

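### The photographic review counts a recognised side as success without recording whether it looked better or worse

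*Protocol*

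**What the plan says.** Protocol Section 4.3.3.7 sets up a review by three blinded readers of each subject's images before and after treatment. It names one response: "Each blinded reviewer will choose which side of the chest was treated with Renuvion". It then defines the outcome: "Success will be correct identification of treated side of the chest by at least 2 of the 3 reviewers".

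Section 4.3.2, item 9, describes the endpoint in the same terms: "Baseline images compared to Day 30, 90, and 180 images will be assessed for correct identification of Renuvion-treated side by blinded IPRs". The synopsis and Section 4.1 agree, and place the reading after the Day 180 visit.

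Other places that bear on the point:

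- **Purpose.** Section 2.2.2 says the study is run to "determine if there is a possible benefit of using the Renuvion APR device". Section 3 adds effectiveness and possible support for a pivotal study.
- **Visible harms.** The device risks in Section 2.2.1 include "pigmentation changes, increased healing time, unsatisfactory scarring, asymmetry and/or unacceptable cosmetic result".
- **Investigator rating.** Section 4.3.3.5: "The PGAIS must be performed by the principal investigator, sub-investigator or qualified clinician delegated by the principal investigator". No blinding is stated for this rater.
- **Subject blinding.** Section 7.2: "The subjects will be blinded as to which side has been treated with Renuvion". Subjects complete the SGAIS and, at Day 180, the satisfaction questionnaire in Attachment A. Items 3 to 7 of that questionnaire ask about satisfaction by side and which side is better.
- **Role of the endpoint.** The primary endpoint is adverse events (Section 4.3.1). The analysis is descriptive (Section 10.1), in up to 10 treated subjects (Section 10.2).

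**The concern.** Naming the treated side correctly shows that the two sides can be told apart. It does not show that the treated side is the better one. A reviewer who picks a side for its tighter skin and a reviewer who picks it for a scar, a change in pigmentation or an asymmetry give the same answer, and both count as success.

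The study looks for a possible benefit, and these reviewers are its only independent third-party raters for whom blinding is stated. A report that most subjects were successes on this endpoint would invite a reading of benefit that the data cannot support. Nor can the analysis plan repair this afterwards: if the reviewers were never asked for direction, only a second reading could supply it.

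**Working it through.** The protocol states no benchmark, power or expected rate for this endpoint, so there is no figure of its own to reproduce. The check has three parts.

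**1. Who gives direction, and who is blinded**

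| Source | Gives direction? | Blinding to side |
|---|---|---|
| Photographic reviewers (4.3.3.7) | No, only which side was treated | Stated |
| PGAIS, site clinicians (4.3.3.5) | Yes | None stated |
| Pinch thickness, chest measurements, grade (4.3.3.1 to 4.3.3.4) | Yes, as measured change | None stated |
| SGAIS and questionnaire, subjects (4.3.3.5, Attachment A) | Yes | Stated, but self-rating |
| Adverse events by side (4.3.1) | Harm only | None stated for the investigator who classifies them |

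Blinded direction comes only from the subjects themselves. Independent, blinded, third-party direction is not collected.

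**2. What the 2-of-3 rule returns**

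Let p be the probability that one reviewer names the treated side, with reviewers independent. The rule is met with probability

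f(p) = 3p²(1 − p) + p³.

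This depends on p alone and not on why the side was named. At p = 0.8, f = 3 × 0.64 × 0.2 + 0.512 = 0.896, whether the side was recognised as improved or as harmed.

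Now suppose the treated side is visibly worse, and p is the chance that a reviewer attributes the worse side to Renuvion. The protocol gives no such rate, so a range is assumed:

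| p | f(p) |
|---|---|
| 0.3 | 0.216 |
| 0.5 | 0.500 |
| 0.7 | 0.784 |
| 0.9 | 0.972 |

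Harm can therefore raise the count well above chance, or push it below chance if reviewers expect tightening and name the better-looking side. Section 4.3.3.7 gives no rule for attribution, so the reader of the result cannot know which applied.

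For context, guessing (p = 0.5) gives 10 × 0.5 = 5 expected successes in 10 subjects. From Binomial(10, 0.5), 7 or more successes arise in 17.2% of studies and 8 or more in 5.5%.

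**3. How a preference question would behave at this size**

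Suppose there is no effect and each reviewer answers no difference with probability q, otherwise choosing either side equally. The chance of choosing a given side is (1 − q)/2, and a given side gets at least 2 of 3 votes with probability f((1 − q)/2). Let D be the number of subjects with a majority for the Renuvion side minus the number with a majority for the untreated side. Its expectation is 0 and its variance is 10 × 2f. Tail probabilities come from exact convolution over 10 independent subjects.

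| q (assumed) | f per side | Expected per side, of 10 | SD of D | P(D ≥ 4 or D ≤ −4) |
|---|---|---|---|---|
| 0 | 0.500 | 5.0 | 3.16 | 0.344 |
| 1/3 | 0.259 | 2.6 | 2.28 | 0.122 |
| 0.5 | 0.156 | 1.6 | 1.77 | 0.045 |

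The measure shows direction and has a clear no-effect value, but it is imprecise with 10 subjects.

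**The case against.** The endpoint is defined consistently wherever it appears, and it is a legitimate measure of detectability. No passage equates success with benefit. Direction is already collected by side in the PGAIS, SGAIS, questionnaire, caliper and chest measurements and adverse events. With at most 10 subjects, each identification can be read against that subject's other results. Section 4.3.3.7 also speaks of a qualitative review, and a reading form not shown here might record more. The 22% to 97% range rests wholly on assumed attribution rates and straddles chance. The proposed preference count is noisy, and asking for preference first may anchor the identification answer. No decision depends on the count.

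Much of this stands as a limit on weight. The ambiguity exists only when this endpoint is read alone, harm may lower the count as well as raise it, and 10 subjects will not settle the matter.

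It does not remove the point. The mention of a qualitative review names no response other than the choice of side, and every description of the endpoint is confined to identification. Reading the count against other results means relying on raters with no stated blinding or on the subjects themselves. A count that harm may move either way is no easier to interpret than one it only raises. Anchoring is a minor cost: with no effect, identification still has a 50% chance level whichever question comes first.

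**Conclusion.** The concern holds. As defined, the photographic endpoint measures whether a difference between sides is visible, and its success count cannot separate benefit from recognisable harm. With a visibly worse treated side, the rule would be met in anything from 22% to 97% of subjects as the attribution rate runs from 30% to 90%. That range is assumed and treats reviewers as independent. The finding itself rests on the wording of Section 4.3.3.7 and not on those figures.

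The reach is limited to one of nine additional endpoints in a descriptive pilot. The primary endpoint is unaffected, and no test or go/no-go rule uses the count. It should be fixed because the change is cheap and the missing answer cannot be recovered by analysis.

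**What to change.** Amend Section 4.3.3.7, and item 9 of Section 4.3.2 and of the synopsis outcome measures to match, before the reading that follows Day 180:

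1. On each image set, the same three reviewers first answer which side looks better: right, left or no difference. That answer is locked before the second question appears.
2. They then name the side they believe was treated, as now.
3. Report by visit, with Day 180 as the main one, the number of subjects in whom at least 2 of 3 preferred the Renuvion side, next to the number in whom at least 2 of 3 preferred the untreated side. State that the expected difference is 0 if there is no effect, and that it is imprecise with 10 subjects.
4. Keep side identification as a descriptive measure of visibility, shown against its 50% chance level, and drop the label of success.

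The cost is one extra answer per image set, a form that locks the first answer, and two or three sentences of text. Reviewers, photographs, timing and sample size do not change. There are two downsides. The favourable count will probably be lower, because no difference does not count towards it, and the first answer may influence the second.

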#### 4.3.3.8 ADVERSE EVENT REPORTING

The definitions of Adverse Events (AEs) and the subtypes are provided in **Section 8** of this study protocol. Adverse events will be classified by the investigator as to:

- Anticipated vs unanticipated
- Serious vs not serious
- Expected Treatment Effect (ETE) vs Adverse Event (AE)
- Severity: mild, moderate, severe
- Device causality: not related, related, undetermined
- Procedure causality: not related, related, undetermined.

### 5. SUBJECT ENROLLMENT AND WITHDRAWAL

#### 5.1 STUDY POPULATION

The study population will consist of males between 18-75 years of age who have chosen to participate in this clinical trial as evidenced by execution of the informed consent document and who meet eligibility criteria defined in this protocol. Subjects will be considered enrolled into the study when they have signed an approved informed consent form. Subjects who are enrolled and do not meet eligibility criteria will be exited as a screen fail without study treatment.

##### 5.1.1 INFORMED CONSENT

Informed consent will be obtained from all subjects prior to study participation. Informed consent is a process that is initiated prior to the individual's agreeing to participate in the study and continues throughout the individual's study participation. Extensive discussion of risks and possible benefits of participation will be provided to each participant.

Investigators have ethical and legal responsibilities to ensure that the protocol is clearly explained to each subject considered for enrollment in the study. Compliance with this requirement should be documented on a written Informed Consent Form approved by the reviewing IRB. Each Informed Consent Form will include the elements required by FDA regulations in 21 CFR Part 50.

Consent forms will be IRB-approved, and the participant will be asked to read and review the document. The investigator, or investigator-delegated study personnel, will explain the research study to the participant and answer any questions that may arise. All participants will receive a verbal explanation in terms suited to their comprehension of the purposes, procedures, and potential risks of the study and of their rights as research participants. Participants will have the opportunity to carefully review the written consent form and ask questions prior to signing. The participants should have the opportunity to discuss the study with their surrogates or think about it prior to agreeing to participate. The participant will sign the informed consent document prior to any procedures being done specifically for the study.

The IRB-approved Informed Consent Form will be signed by the study personnel obtaining consent. A copy of the informed consent document will be given to the participants for their records. The investigative site will keep the

original on file. The rights and welfare of the participants will be protected by emphasizing to them that the quality of their medical care will not be adversely affected if they decline to participate in this study.

The participants may withdraw consent at any time throughout the course of the trial without any penalty or loss of benefits to which the subject is otherwise entitled. An Investigator may also discontinue a subject from the study without the subject's consent, if the Investigator feels it is in the best medical interest of the subject.

#### 5.1.1.1 CONSENT/ASSENT AND OTHER INFORMATIONAL DOCUMENTS PROVIDED TO PARTICIPANTS

Consent forms describing in detail the study device, study procedures, and risks are given to the participant and written documentation of informed consent is required prior to starting intervention/administering study product.

#### 5.1.2 PRE-TREATMENT RECRUITING/SCREENING

Subjects will be recruited from the study site's patient database and/or with the use of an IRB-approved form of advertising. Study site personnel will explain the design and purpose of the study to potential study subject. Subjects interested in participating and who qualify will visit the study site where informed consent will be obtained.

##### 5.1.2.1 SCREEN FAILURES

A screen failure subject is one from whom informed consent is obtained and is documented in writing (i.e., subject signs an Informed Consent Form), but who does not receive a study treatment because of failure to meet all the eligibility criteria. Screen failure subjects will be included in the total number of subjects enrolled (i.e., all subjects consented), but not counted towards the total subjects treated.

### 5.2 INCLUSION CRITERIA

Subjects must meet all the following criteria for study enrollment:

- Male subjects, ages 18 – 75 years old.
- [ASA Physical Status Classification System](#) Class I and Class II subjects.
- Clinical diagnosis of primary Gynecomastia.
- Gynecomastia Rohrich Grade IIA or higher.
- Symmetrical gynecomastia Rohrich grades.
- Symmetrical chest measurements (no more than 3% variance between sides).
- Scheduled for Gynecomastia surgery.
- Willing to have Renuvion APR System as an adjunct procedure on one side understanding that an optional balancing procedure may be provided post-study exit.
- Understands and accepts the obligation not to undergo any other procedures or treatments in the areas to be treated during study participation.
- Absence of physical conditions unacceptable to the investigator.
- Willing and able to comply with protocol requirements, including study-required images/photos, assessments/measurements, and returning for follow-up visits.
- Willing to release rights for the use of study photos, including in publication.
- Able to read, understand, sign, and date the informed consent.

### 5.3 EXCLUSION CRITERIA

Subjects will be excluded if they meet any of the following criteria:

- Subjects without clinical diagnosis of primary Gynecomastia and/or a clinical diagnosis of gynecomastia with secondary causes such as medications, drugs, or testicular tumors.
- Subjects presenting with ASA Physical Status Classification System Classes III or higher.
- Gynecomastia Rohrich Grade I.
- Non-symmetrical gynecomastia Rohrich grades.

- Non-symmetrical chest measurements (more than 3% variance between sides).
- Previous treatment or surgery in the breast area.
- Active systemic or local skin disease that may alter wound healing.
- Significant or uncontrolled medical condition that in the opinion of the investigator participation in the study may compromise the patient's health.
- History of autoimmune disease (excluding Hashimoto's thyroiditis).
- Known susceptibility to keloid formation or hypertrophic scarring.
- Cancerous or pre-cancerous lesions in the area to be treated.
- Possesses a surgically implanted electronic device (i.e. pacemaker).
- Serious mental health illness such as dementia or schizophrenia; psychiatric hospitalization in the past two years.
- Use of endermology post-procedure for the duration of the study.
- Participation in any other investigational study within 30 days prior to consent and throughout study participation.
- Subject who, in the opinion of the investigator, is not an appropriate candidate for the study.

